Research Methodology: We hypothesize that: the GABAA benzodiazepine partial inverse agonist, iomazenil, will attenuate several measures of ethanol intoxication in healthy human subjects. In a double-blind, placebo-controlled fashion, counterbalanced, within-subjects design, participants will receive an intravenous (IV) infusion of placebo or active ethanol (target BrAc=100mg%) followed by placebo or active iomazenil (3.7 μg/kg) administered intravenously via a separate IV. Subjects will undergo four test days. Subjects will receive the following drug combinations: (1) active ethanol and active iomazenil; (2) active ethanol and placebo iomazenil; (3) placebo ethanol and active iomazenil; and (4) placebo ethanol and placebo iomazenil. Measures of intoxication will be collected before, and several times during and after drug administration. Automobile driving will be assessed using a driving simulator. Cognitive function will be assessed using the visual novelty oddball paradigm. EEG will be recorded during the driving simulator and novelty oddball tasks, allowing for the analysis of ERP components related to making errors (error-related negativity, ERN; driving simulator) and target (P3b)

Innovation and Impact: Although inverse agonists have been shown to attenuate several aspects of ethanol in animals, this has not yet been demonstrated in humans. The innovative elements of the study are:1) the use of the only BZ inverse agonist probe available for use in humans – one that was developed at this center and to our knowledge is not available elsewhere for use at pharmacological doses, 2) the use of event- related potential and event-related oscillations, 3) the use of simulated driving, a functional measure of ethanol effects, and driving error-related potentials, 4) the use of eyeblink conditioning as a biomarker of alcohol's effects on cerebellar function. This study may provide insights into the neurobiology through which iomazenil attenuates features of ethanol intoxication in humans. In so doing, this project may help to advance the exploration of benzodiazepine inverse agonists as ethanol "antidotes" and possible treatments for pathological alcohol use. Characterizing the interplay of iomazenil-ethanol interactions on several overlapping measures will contribute to the rational development of agents similar to iomazenil as antidotes or pharmacotherapies for alcoholism.

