To determine whether iomazenil, attenuates the “buzzed” feeling state of ethanol intoxication in healthy human subjects. We expect that the behavioral data will not conform to normality as in our previous studies. Therefore, a nonparametric analysis for repeated measures data will be conducted with ethanol (active or placebo), iomazenil (active or placebo) and time as within-subject factors. The analysis will be performed by rank transforming the data, then fitting a mixed-effects model with an unstructured variance-covariance matrix using PROC MIXED in SAS (SAS Institute Inc, Cary, NC), and finally adjusting the P values for the analysis of variance-type statistics (ATS). One of the advantages of this approach is that it uses all available data on each subject including dropouts. If the 3-way interaction among ethanol, iomazenil, and time are significant, contrasts for testing interactions between iomazenil and ethanol will be performed at each time point. For the points where significant interactions are observed, the simple effects of ethanol, and iomazenil will be tested to determine the nature of the interaction. Bonferroni corrections will be applied for multiple analyses within, but not across, domains.

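### The iomazenil comparison on active-ethanol days ignores each day's own ethanol response before iomazenil: a loss of precision and a missing comparability check, not a bias

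*SAP*

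**What the plan says.** The protocol (Research Methodology) describes a "counterbalanced, within-subjects design" in which each of the four drug combinations has its own day: "Subjects will undergo four test days". Within a day, subjects receive "placebo or active ethanol (target BrAc=100mg%) followed by placebo or active iomazenil", the second drug through a separate line. On timing it says: "Measures of intoxication will be collected before, and several times during and after drug administration". It does not name a rating between the start of ethanol and the start of iomazenil.

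The SAP paragraph on the buzzed feeling state ranks the data and fits a mixed model "with ethanol (active or placebo), iomazenil (active or placebo) and time as within-subject factors", with an unstructured covariance matrix and ATS-adjusted P values. Testing is sequential. A significant three-way interaction leads to an ethanol-by-iomazenil contrast at each time point. Where that contrast is significant, "the simple effects of ethanol, and iomazenil will be tested to determine the nature of the interaction". No covariate, change score or contrast against an earlier rating on the same day is specified. The SAP's opening paragraph mentions a baseline session, but only in connection with order effects.

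**The concern.** Until iomazenil starts, the two active-ethanol days are treated identically. A rating in that window therefore measures the day's ethanol response before iomazenil can act. A sober rating before any drug cannot do this, because a buzzed score should then be close to zero on every day.

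The iomazenil effect on active-ethanol days is the direct measure of attenuation, which is the aim of this analysis. As planned, it is the difference between two days at one time point. All day-to-day variation in ethanol response stays in its error, including the part that a pre-iomazenil rating could explain. Nor does any planned report show whether the two days were already different before iomazenil. What is at stake is the width of the interval for the attenuation estimate, and how convincingly a difference can be attributed to iomazenil.

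**Working it through.** **Inputs.** The order of infusions, separate days, counterbalancing and rating times come from the protocol. The model, the gating and the two-sided 0.05 level come from the SAP. Neither document gives a sample size, SD, correlation or effect size, so there is no stated figure to reproduce, and every value below is an assumption.

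**1. Does the planned model already adjust?** No. With complete data, an unstructured covariance matrix leaves the contrast at one time point equal to the difference of two cell means. The earlier rating does not enter it.

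**2. Variance.** Let r be the within-subject, same-day correlation between the pre- and post-iomazenil ratings on ethanol. Regressing the between-day difference on the same difference before iomazenil multiplies the contrast's variance by 1 − r²:

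| r | 1 − r² | N for 80% power at 0.5 SD of the paired difference |
|---|---|---|
| planned | 1 | 32 |
| 0.3 | 0.91 | 29 |
| 0.5 | 0.75 | 24 |
| 0.7 | 0.51 | 17 |

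N is ((1.96 + 0.84)/0.5)² × (1 − r²), rounded up. A simple change score has variance ratio 2(1 − r), so it helps only above r = 0.5.

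Estimating the slope costs an expected factor of (n − 2)/(n − 3), which is 18/17 = 1.06 at n = 20. Break-even is r² = 1/(n − 2) = 1/18, or r = 0.24.

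**3. Power of the iomazenil comparison taken alone.** Assumed: 20 subjects, a 0-100 scale, mean 50 on ethanol, iomazenil effect −12. Day and residual SDs of 7/12, 10/10 and 12/8 give r = 49/193 = 0.25, 100/200 = 0.50 and 144/208 = 0.69.

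In rating points at r = 0.50, the planned SE is √(2 × 200/20) = 4.47. The adjusted SE is 4.47 × √(0.75 × 18/17) = 3.99, about 11% smaller. Noncentral t power for 12/4.47 on 19 df is 72%, and for 12/3.99 on 18 df it is 81%. At r = 0.69 the same steps give 70% and 92%.

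On pooled ranks, as the SAP specifies, simulation gives about 65% rising to 73% at r = 0.50 and to 83% at r = 0.69, with no gain at r = 0.25. Adjusting for the sober rating instead gives 61%, also no gain.

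**4. Type I error.** With normal data, n of 12, 20 or 40, and correlations of 0.3 to 0.9, both the planned and the adjusted test reject in 4.8-5.2% of null trials.

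**5. Given a chance imbalance.** Suppose the two active-ethanol days happen to differ by 2 SE before iomazenil and iomazenil does nothing. The planned test then rejects with probability 1 − Φ((1.96 − 2r)/√(1 − r²)) + Φ((−1.96 − 2r)/√(1 − r²)). This is 0.13 at r = 0.5 and 0.22 at r = 0.7. With no such imbalance it is 0.02 and 0.01. Over all samples it averages 5%.

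**6. The whole sequence.** This was simulated on ranks with three rating times and a Hotelling test standing in for the ATS step, without Bonferroni adjustment. With noisy placebo-ethanol ratings (85% zeros, otherwise 1-7), power to pass all three steps moves only from about 9% to 9-11%. The two-way contrast on pooled ranks is the bottleneck: 27% planned, 26% adjusted. If placebo-ethanol ratings all sit at the floor, power of the sequence rises from about 54-57% to 60-72%. In that case the tied placebo ranks cancel and the two-way contrast equals the simple effect, so the gain appears only if the covariate is in both.

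**The case against.** A reader might infer that day-to-day swings can pass as an iomazenil effect, or that test-day order can bias the comparison. The documents do not support this. Order is counterbalanced, dosing is double-blind, the SAP tests for order effects, and the swings are in the error term, so the error rate stays near 5%. Step 5 describes chance imbalance in a particular sample, which the 5% level already covers. It is a reason to report the pre-iomazenil comparison, not evidence of bias.

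The second objection is that the SAP never runs the simple effect on its own. It follows two interaction tests, so the gain from about 65% to 83% must not be read as the gain in the trial's power. That stands; step 6 gives the relevant figures.

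Third, the three-way interaction already uses change within the day. That is true, but the screen is incomplete. If the time factor includes a pre-ethanol rating, a swing in ethanol response also varies with time. With 20 subjects, a real 0.7 SD shift on one active-ethanol day that began before iomazenil passed this step 23-28% of the time.

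Finally, a rating in the required window is likely from the protocol's wording but is not stated, and the benefit depends on a correlation the documents do not give. Both points stand.

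**Conclusion.** The point holds as a matter of efficiency and reporting. The SAP leaves out a same-day measure of ethanol response that the order of infusions makes available. The main benefit of using it is a narrower interval for the attenuation estimate: the contrast's variance falls by about 25% at r = 0.5 and 49% at r = 0.7, before the small cost of estimating the slope. Near r = 0.25 with 20 subjects there is no gain.

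Whether the gated rank-based sequence gains power depends on the placebo-ethanol days: hardly at all if those ratings are noisy, and by roughly 6 to 15 percentage points (54 to 60, 57 to 72) if they sit at the floor. All of this rests on assumed sample size, SDs, correlation and effect. It is a cheap improvement of modest priority.

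**What to change.** In the SAP paragraph on the buzzed feeling state:

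- Name the last rating on ethanol before that day's iomazenil infusion as a day-level covariate, ranked in the same way as the outcome if the analysis stays on ranks.
- For each post-iomazenil time point, use it to estimate iomazenil against placebo on active-ethanol days, with a confidence interval. The direct form regresses each subject's between-day difference on the same difference before iomazenil.
- Use the corresponding covariate in the ethanol-by-iomazenil contrast. Otherwise the unadjusted contrast still decides whether the simple effect is reached.
- Report the pre-iomazenil difference between the two active-ethanol days as a descriptive check.
- If no rating falls in that window, time one of the planned ratings during administration to fall there.

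The cost is SAP wording, one degree of freedom and at most one re-timed self-rating. The downside is a trivial loss of precision if the same-day correlation is about 0.25 or less.

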Ability of Partial Inverse Agonist, Iomazenil,
to Block Ethanol Effects in Humans

NCT01590277

June 10, 2022

ABILITY OF PARTIAL INVERSE AGONIST, IOMAZENIL, TO BLOCK ETHANOL EFFECTS IN HUMANS

Principal Investigator: [name] [name]

Statistical Analysis Plan: All data will be transcribed onto respective teleforms, checked for completeness and clarity. Continuous variables will be checked for normality using normal probability plots and Kolmogorov- Smirnov statistics. Transformations will be applied if necessary. A criterion of $P < 0.05$ will be used throughout to determine statistical significance. In the mixed models described below, the correlation between repeated measures on an individual will be modeled using random effects and/or structured variance-covariance matrices. The best-fitting variance-covariance structure will be determined by information criterion. The mixed-effects approach is advantageous in that it is unaffected by randomly missing data and allows greater flexibility in modeling the correlation structure of repeated-measures data. We will test for order effects, although any such effects should be greatly minimized with the inclusion of the baseline session. All tests will be two-sided and considered statistically significant at $\alpha=.05$. Significance levels for secondary comparisons will be adjusted for multiple tests using the Bonferroni correction, basing the adjustment on the number of conceptually related statistical tests within each hypothesis.

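### Single-step Bonferroni within each domain or hypothesis is valid, but Holm's step-down version gives the same 5% bound and rejects at least as much: a modest, optional gain

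*SAP*

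**What the plan says.** The SAP's opening paragraph sets a two-sided 5% level and adds: "Significance levels for secondary comparisons will be adjusted for multiple tests using the Bonferroni correction". It describes the size of each correction in these words: "basing the adjustment on the number of conceptually related statistical tests within each hypothesis". The paragraph on the 'buzzed' feeling state ends: "Bonferroni corrections will be applied for multiple analyses within, but not across, domains". No step-down method is mentioned, so single-step Bonferroni is what is planned.

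The 'buzzed' analysis runs in three stages. First comes the 3-way test, and the follow-up depends on its result: "If the 3-way interaction among ethanol, iomazenil, and time are significant". When that condition is met, the second stage is that "contrasts for testing interactions between iomazenil and ethanol will be performed at each time point". Last, at the points with a significant interaction, "the simple effects of ethanol, and iomazenil will be tested to determine the nature of the interaction".

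The Protocol (Research Methodology) indicates that there are several time points: "Measures of intoxication will be collected before, and several times during and after drug administration". Their number is not given. Neither document lists the domains or says which tests make up a family.

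**The concern.** Bonferroni holds every test in a family to the strictest threshold, even after some hypotheses in that family have been rejected. Holm relaxes the threshold after each rejection without weakening the familywise guarantee. Where the plan corrects a fixed family of two or more tests, Bonferroni can therefore leave a real effect undeclared that Holm would declare at the same error bound.

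At stake is how fully the trial can describe when iomazenil attenuates the 'buzzed' state. The time-point contrasts give that description and also decide where simple effects are examined, so a missed time point loses its simple effects too.

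**Working it through.** **Inputs.** The level is 0.05, two-sided (SAP, opening paragraph: "A criterion of $P < 0.05$ will be used throughout to determine statistical significance"). The number of tests m, the sample size, the effects and the correlation between time points are not in the documents. Everything about size below is assumed.

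**1. The plan's own level.** Bonferroni tests each of m hypotheses at 0.05/m, and m × 0.05/m = 0.05 for every m. With m = 4 and independent tests the familywise error is 1 − (1 − 0.0125)^4 = 0.0491. The planned correction does what it is meant to do.

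**2. Holm on the same family.** The ordered p-values are compared with 0.05/m, 0.05/(m−1), …, 0.05, stopping at the first failure.
- *Same bound.* Suppose m0 hypotheses are true nulls. When the first of them is rejected, at most m − m0 false ones have gone before, so the threshold in force is at most 0.05/m0. The chance that any of m0 null p-values falls below 0.05/m0 is at most m0 × 0.05/m0 = 0.05, whatever the dependence.
- *Rejects at least as much.* The first threshold equals Bonferroni's and all later ones are larger.
- *Example, m = 4, p = 0.004, 0.015, 0.02, 0.04.* Bonferroni (0.0125) rejects one. Holm (0.0125, 0.0167, 0.025, 0.05) rejects all four.

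**3. Size if the family is the time-point contrasts.** Simulation with equicorrelated normal statistics. Contrasts were tested only if a chi-square test of equal interaction over time was significant at 5%; this stands in for the planned rank-based test. The grid had 4, 6 or 8 time points, one to all of them affected, noncentrality 1 to 4, and correlation 0 to 0.75: 504 settings.

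| Quantity | Gain per true contrast (percentage points) |
|---|---|
| Median over settings | 0.5 |
| 75th / 90th percentile | 2.1 / 4.1 |
| Largest (8 points, 7 affected; 60.2% to 67.8%) | 7.6 |
| Share of settings under 1 / under 2 | 59% / 73% |
| Bonferroni detection 30–80%, half or more but not all points affected | median 3.8, 10th–90th percentile 2.0–6.1 |
| One point affected | at most 0.13 |
| Effect constant over time | at most 0.51 |

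With 10 or 12 time points the largest gain was 8.8. At correlation 0.5, the profile (0, 2, 3, 4) went from 62.0% to 66.2%, and (0, 2, 3, 4, 3, 2) from 51.2% to 56.6%. Weak profiles peaking at 2 gained 0.2 to 0.7. With t-tests at an assumed 20 or 40 subjects and a rise-and-fall effect, the median gain was 0.2, and 28 of 32 settings were under 2. The chance of detecting at least one affected point rose by at most 0.13. Familywise error under partial nulls was at most 4.4% (Bonferroni) and 4.9% (Holm). No Bonferroni rejection was lost.

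**4. Size if the family is several measures in a domain.** No preceding test; noncentrality 2.8, about 80% unadjusted power. For two independent real effects, single-test power is 0.7118 at level 0.025 and 0.7995 at 0.05. Holm's power per test is 0.7118 + (0.7995 − 0.7118) × 0.7118 = 0.774, against 0.712 for Bonferroni. For four real effects it is 61.9% to 72.6%. For two real out of four it is 62.0% to 64.5%.

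**5. The simple-effect stage.** Testing two simple effects per flagged point and pooling over points gives a first threshold of 0.05/4 = 0.0125 with two points flagged and 0.05/6 = 0.0083 with three. Because Holm can flag more points, this family can grow. Over 48 settings, the share of trials losing a simple-effect rejection they had under Bonferroni throughout was up to 2.1% if the pooled step stays Bonferroni, and up to 0.11% if it is Holm.

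A separate two-test family at each flagged point removes that loss but not the error. Assume 4 to 8 time points, all but one affected, and no true iomazenil effect under ethanol, with the interaction arising under placebo ethanol. The chance of at least one false claim that iomazenil works under ethanol was then 5% to 16%, against 1.2% to 1.8% with Bonferroni pooled over flagged points.

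**The case against.** The strongest reply is that nothing here is wrong: Bonferroni is valid, the median simulated gain is half a point, the test that opens the follow-up is unaffected, and the advantage of Holm is general rather than specific to this trial. This stands, and it limits the point to an optional improvement. A reader might infer that the plan is in error or needlessly strict. The documents do not support that. With no correction across domains, the slack inside each domain also gives some protection, and Holm uses part of it: with m = 4, half the nulls true and independent tests, familywise error goes from 2.5% to 3.9%, still within the bound.

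A second reply is that the family is unknown. That also stands. The quoted sentence may mean time-point contrasts or several measures. The direction of the gain is the same under both readings, but its size is not. Shares of an assumed grid are not probabilities for this trial, and gains near 10 points need every measure to be real at good power with no preceding test.

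A reader might also infer that the simple effects can be corrected within each flagged time point at no cost in error. Step 5 shows otherwise. Nor does the SAP say that there are two such effects: a 2 × 2 layout has four. With four tested at two flagged points, the pooled family is 8 tests and the first threshold is 0.05/8 = 0.00625.

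**Conclusion.** The point holds as a small efficiency gain. That Holm dominates Bonferroni on a fixed family needs no assumption about this trial. How much it would add here depends wholly on assumed time points, effects and correlations. On the time-point reading the gain is 0 to about 8 points per true contrast and usually under 1. Holm helps to identify further affected time points once one has been found; it does little to find the first.

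The 5% bound applies within each family. It does not extend across domains or across the three stages. It is also stated for families fixed in advance, whereas the simple effects are selected from the data under either method.

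**What to change.** Optional. In the SAP's opening paragraph and in the 'buzzed' paragraph, replace Bonferroni with Holm for the ethanol-by-iomazenil time-point contrasts and for the other within-domain or within-hypothesis families. Leave the 3-way test and the families as they are, and list the tests in each family, which is needed under either method.

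Do not cut the simple-effect family down to each flagged time point as part of this change. If the simple effects are pooled over flagged points, apply Holm to that pooled family and count every simple effect actually tested, up to four per time point. Accept the very small chance of losing a simple-effect rejection because more points are flagged: about 0.1% of simulated trials, with two effects per point. State that the 5% bound holds within each family only.

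The cost is SAP wording; the data, models, contrasts and raw p-values stay the same. The SAP is dated June 10, 2022, and the documents do not say whether the data are still blinded. Make the change only before unblinding. Otherwise keep Bonferroni as planned and show Holm-adjusted p-values as a labelled supplementary result.

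### Do the SAP's two Bonferroni sentences conflict, and does leaving domains uncorrected against each other undermine the trial's claim?

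*SAP*

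**What the plan says.** The general paragraph of the SAP sets the nominal level: a criterion of P < 0.05 "will be used throughout to determine statistical significance", with all tests two-sided. It then adds: "Significance levels for secondary comparisons will be adjusted for multiple tests using the Bonferroni correction", and defines the family by "basing the adjustment on the number of conceptually related statistical tests within each hypothesis".

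The second SAP paragraph opens with its own aim, the buzzed feeling. It plans a rank-based mixed model with ethanol, iomazenil and time as within-subject factors. Contrasts at each time point follow only if the three-way interaction is significant. The paragraph closes with: "Bonferroni corrections will be applied for multiple analyses within, but not across, domains".

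The protocol's Research Methodology section states one general hypothesis, that iomazenil "will attenuate several measures of ethanol intoxication in healthy human subjects". The protocol mentions subjective intoxication, simulated driving, the visual novelty oddball task, the ERN and P3b components from EEG, and eyeblink conditioning. Neither document defines or counts domains, lists the hypotheses, or says which comparisons are primary and which secondary.

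**The concern.** Read quickly, the two Bonferroni sentences use different units. One counts tests inside a hypothesis, the other counts analyses inside a domain. Since the protocol writes only one hypothesis, the first sentence could pool every outcome into one family, which the second sentence rules out. With five outcomes, a driving or ERP result with p between 0.01 and 0.05 would then be significant under one sentence and not under the other.

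The second worry does not need a contradiction. With no correction across domains and no primary outcome, each domain can be tested at the full 0.05. If a success in any one of them were reported as showing that iomazenil attenuates intoxication, the error rate of that claim would be well above 5%.

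**Working it through.** **Inputs.** The two-sided level of 0.05 per test is from the SAP. The number of domains, k, is in neither document. Three to five is assumed from the outcomes mentioned in the protocol. Correlation between outcomes is not given either, so a range of 0 to 0.8 is used. The documents state no family-wise rate, so there is no figure of the plan's own to reproduce.

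**Step 1: the two thresholds.** Bonferroni gives 0.05/k:

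- k = 1: 0.05
- k = 2: 0.025
- k = 3: 0.0167
- k = 4: 0.0125
- k = 5: 0.01

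The pair 0.05 and 0.01 therefore requires one family of one test and another of exactly five. Counting five means treating ERN and P3b as separate domains, although both are ERP components and the ERN is recorded during the driving task.

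**Step 2: the two sentences side by side.** The general rule does not count every test under a hypothesis. It counts the conceptually related ones. It also speaks of each hypothesis, which implies more than one, and the second SAP paragraph begins with a specific aim of its own. If each aim is a hypothesis, or if a domain is a set of conceptually related tests, the families coincide. The general rule also covers only secondary comparisons, so a test treated as primary faces 0.05 under that rule as well. The statement about P < 0.05 is the nominal level to which the adjustment is applied, not a third rule.

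**Step 3: false-positive rate across domains.** All nulls are taken as true, with one test at 0.05 per domain.

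- At least one positive, independent domains: 1 − 0.95^k. For k = 3, 1 − 0.8574 = 14.3%. For k = 4, 1 − 0.8145 = 18.5%. For k = 5, 1 − 0.7738 = 22.6%.
- At least two positive, independent domains: 1 − 0.95^k − k × 0.05 × 0.95^(k−1). For k = 3, 1 − 0.8574 − 0.1354 = 0.7%. For k = 5, 1 − 0.7738 − 0.2036 = 2.3%.

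For correlated domains, the same probabilities come from numerical integration over a common normal factor (equicorrelated test statistics):

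| Correlation | At least one, k = 3 to 5 | At least two, k = 3 to 5 |
|---|---|---|
| 0 | 14.3% to 22.6% | 0.7% to 2.3% |
| 0.5 | 12.5% to 18.3% | 2.1% to 4.8% |
| 0.8 | 9.8% to 12.7% | 3.8% to 6.1% |

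The outcomes come from the same subjects and the protocol itself describes them as overlapping, so independence is the least likely row.

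**Step 4: which column applies.** The left column needs a rule that one positive domain establishes the general hypothesis. No such rule is written. The hypothesis refers to several measures; if that means at least two, the right column applies and the rate is near or below 5%. If each domain supports only a claim about itself, each claim carries its own 5% and neither column is the relevant error rate.

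**The case for a change.** The strongest reply is that the documents leave all of this open. They do not say that one domain is enough, but they do not say that it is not, and with no primary test named any domain could be put forward afterwards as the main result. Even at correlation 0.8 the chance of at least one false-positive domain is about two to two and a half times 0.05. Naming a single primary contrast on the buzzed feeling and placing the other outcomes in one Holm-corrected family would cost only SAP wording and a first-step threshold of 0.05/4 = 0.0125 for four secondary outcomes.

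The arithmetic in that reply stands, and so does the remark that the terms are undefined. The remedy, however, is more than a matter of wording. It chooses a primary outcome on the sponsor's behalf. It replaces the planned order of testing, three-way interaction first and time-point contrasts after, with a different contrast. It also reverses a choice that the SAP makes openly. Whether to correct across distinct outcome domains in a mechanistic study is a question on which experienced statisticians differ: correction protects a global claim but costs power in every domain.

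**Conclusion.** No change to the plan is called for. The two sentences are worded differently but can be read as the same family, and no contradiction is shown. The 0.05 versus 0.01 split rests on an assumed count of five. The rate of roughly 10% to 23% is correct for three to five domains, from correlation 0.8 to independence with all nulls true, but only under a rule that any one positive domain is enough. Requiring two positive domains brings it to 0.7% to 6.1% over the same range.

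The gap in definitions is one that analysts can fill sensibly: treat each outcome area as its own family, correct within it, and let a positive result support a statement about that area only. Leaving domains uncorrected against each other is a disclosed and fair trade-off for a within-subject laboratory study in healthy volunteers. The conclusion would be different if the report used a single positive domain, without correction, as proof of the general hypothesis; nothing in the plan commits the sponsor to that.
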